MedDRA	Independent safety review committee
MMRM	Mixed-effect model repeated measure
PCS	Potentially clinically significant
PK	Pharmacokinetic(s)
PT	Preferred term
SAE	Serious adverse event
SAP	Statistical analysis plan
SD	Standard deviation
SFISD	Start of first infusion of study drug
SOC	System organ class
TEAE	Treatment-emergent adverse event
TFLs	Tables, figures and listings
ULN	Upper limit of normal
WHO	World health organization

1 INTRODUCTION

This statistical analysis plan (SAP) is based on the CM4620-204 Protocol version 8.1 dated 31 March 2021. The plan covers statistical analysis of efficacy and safety data to assess the efficacy and safety of Auxora compared to Placebo in patients with severe COVID-19 Pneumonia. The SAP is for the analysis of Part 2 of the CM4620-204 study.

2 STUDY OBJECTIVES

2.1 Primary Objective

To assess the clinical efficacy of Auxora in patients with severe COVID-19 pneumonia

2.2 Secondary Objectives

- To assess the safety and tolerability of Auxora in patients with severe COVID-19 pneumonia
- To assess the pharmacokinetic profile of Auxora in patients with severe COVID-19 pneumonia

3 STUDY DESIGN

3.1 Overall Study Design

Part 2 is a randomized, double blind, placebo-controlled study in which initially up to 400 patients receiving supplemental oxygen at Screening, and who meet all of the inclusion criteria and none of the exclusion criteria, were to be randomized 1:1 to receive Auxora plus standard of care or Placebo plus standard of care. After a blinded analysis of the mechanical ventilation and death rate in the subgroup of patients with a baseline imputed $\text{PaO}_2/\text{FiO}_2 > 200$ who were randomized into the study, the number of patients in this subgroup were capped at 26. The study sample size remained 320 for patients with a baseline imputed $\text{PaO}_2/\text{FiO}_2 \leq 200$. When enrolling both subgroups, patients were stratified to ensure balanced randomization between the Auxora and Placebo arms.

The dose of Auxora will be 2.0 mg/kg (1.25 mL/kg) administered at 0 hour, and then 1.6 mg/kg (1 mL/kg) at 24 hours and 1.6 mg/kg (1 mL/kg) at 48 hours from the SFISD. The dose of Placebo will be 1.25 mL/kg administered at 0 hour and then 1 mL/kg at 24 hours and 1 mL/kg at 48 hours from the SFISD. The SFISD should occur within 12 hours of the patient or LAR providing informed consent. The dosing will be based on actual body weight obtained at the time of hospitalization or screening for the study. As described in the pharmacy manual, there will be an upper limit of the absolute dose (volume) of Auxora and volume of Placebo that will be administered for patients weighing more than 125kg.

A study physician or appropriately trained delegate will perform assessments at Screening, immediately prior to the SFISD, and immediately prior to each subsequent infusion. At 72 hours after the SFISD, the patient will be assessed every 24 hours (± 4 hours) until 240 hours after the SFISD, then q48 hours until Day 30 after the SFISD, or until discharge if earlier. Patients who are discharged before Day 25 after the SFISD will be followed-up at Day 30 (± 5 days) for a safety and mortality assessment. Patients who are discharged before Day 55 after the SFISD will be followed up at Day 60 (± 5 days) for a safety and mortality assessment.

3.2 Schedule of Study Procedures

Table 1 Schedule of Assessments

	Screen	If Eligible, Baseline Assessment	R	0 hour	24 (± 2) hours	48 (± 2) hours	72 (± 2) hours	96, 144, 192, 240 hours (± 4 hours)	120, 168, 216 hours (± 4 hours)	Days 12-28 ^g (± 4 hours)	Days 30, 60 ^e (± 5 days)	
Informed Consent	X											
Daily Assessment - Ordinal Scale	X				X	X	X	X	X	X	X	
Weight and Height	X											
Vital Signs ^a including SpO ₂ and FiO ₂	X			X ^f	X	X	X	X	X	X	X	
Arterial Blood Gas ^b	X			X	X	X	X	X	X	X	X	
Pathogen Testing-COVID-19 diagnosis	X											
CXR or CT scan of the lungs	X											
Influenza A, B and Respiratory Panel ^c	X											
Daily Laboratory Monitoring ⁱ		X			X	X	X	X	X			
PK Analysis ^h					X	X	X					
Q72 hour Laboratory Monitoring ⁱ		X					X	X	X			
AE/SAE Assessment				X	X	X	X	X	X	X	X	X
Concomitant Medications				X	X	X	X	X	X	X	X	
Randomize patient			X									
Study Drug Administration				X	X	X						
IL-6 and IL-2R ^d		X						X ^d				

Hospitalized patients will complete all assessments. Patients will complete the Day 12 assessment if discharged home on oxygen prior today 12. All patients will complete the Day 30 assessment.

- a. Vital Signs will include temperature, heart rate, respiratory rate, systolic blood pressure, diastolic blood pressure, and SpO₂ by pulse oximetry. For the SpO₂, both the values at the time of the assessment and the lowest noted from the time of the last assessment shall be recorded. The FiO₂ shall be recorded at the time of each SpO₂ recording.
- b. Arterial blood gas results obtained as standard of care shall be recorded.
- c. If performed as local standard of care.
- d. Blood samples for IL-6 and IL-2R will be shipped to a reference lab and results may not be available to the clinical team while managing the patient. The IL-6 and IL-2R will be obtained prior to randomization and again at 96 hours. The IL-6 and IL-2R may be performed on blood drawn in the previous 12 hours.
- e. Day 30 will be phone call assessment for patients who were discharged prior to Day 25. ; Day 60 will be a phone call assessment for patients discharged prior to Day 55
- f. 0-hour vital signs required only if screening vital signs were measured >6 hours prior to SFISD.
- g. Patients discharged prior to Day 12 with the need for supplemental oxygen will be contacted on Day 12 to determine if they are still receiving supplemental oxygen.
- h. PK samples will be drawn at selected sites. Draw blood for PK analysis together with daily laboratory monitoring. The PK specimens may be obtained from blood drawn in the previous 12 hours. The time of the draw must be recorded.
- i. Daily and Q72 hour laboratory monitoring may be performed on blood drawn in the previous 12 hours. Q 72 hours labs will

be performed at 72, 144 and 216 hours

4 SAMPLE SIZE

In the initial design of Part 2 of the study, 320 patients in the baseline imputed $\text{PaO}_2/\text{FiO}_2 \leq 200$ subgroup and 80 patients in the baseline imputed $\text{PaO}_2/\text{FiO}_2 > 200$ subgroup were to have been randomized. A constant recovery rate ratio of 1.43 was assumed for patients receiving Auxora compared to Placebo in both subgroups. In order to provide power of approximate 90% to detect a difference in the recovery rate ratio of approximately 1.43 by a stratified 2-sided log-rank test at an overall 0.05 alpha level, given the 1:1 randomization, it was determined that the study would require 330 recovery events. With the study length of 30 days, the assessment of time to recovery required a sample size of 400 patients.

The enrollment of patients in the subgroup with a baseline imputed $\text{PaO}_2/\text{FiO}_2 > 200$ was stopped early because a blinded analysis of the data from the first 26 patients in the subgroup randomized into the study showed a low rate of mechanical ventilation or death. This finding was consistent with Part 1 of the study where no patients with a baseline imputed $\text{PaO}_2/\text{FiO}_2 > 200$ required mechanical ventilation or died.

The Part 2 study sample size was then reevaluated given that the primary endpoint would focus on the subgroup of patients with a baseline imputed $\text{PaO}_2/\text{FiO}_2 \leq 200$. A two group log-rank test with a 0.05 two-sided significance level would have 90% power to detect a difference in the recovery rate ratio of approximately 1.49 in the 320 patients with a baseline imputed $\text{PaO}_2/\text{FiO}_2 \leq 200$ who were randomized 1:1 to Auxora or Placebo.

To further ensure that the sample size of 320 patients in the baseline imputed $\text{PaO}_2/\text{FiO}_2 \leq 200$ subgroup is an adequate sample size, a sample size re-estimation procedure will be applied when the first 70 patients in the baseline imputed $\text{PaO}_2/\text{FiO}_2 \leq 200$ subgroup have completed or discontinued from the study. The IDMC will perform the procedure and will make a nonbinding recommendation to CalciMedica to increase or not increase the study sample size. No ongoing study patients will be included in this sample size re-estimation procedure. The sample size will be re-estimated to provide a conditional power of 90%, based on the evaluation of the treatment efficacy. The sample size re-estimation procedure will not allow for a reduction in the planned sample size of 320 for the baseline imputed $\text{PaO}_2/\text{FiO}_2 \leq 200$ subgroup. If the study randomizes 600 patients in the baseline imputed $\text{PaO}_2/\text{FiO}_2 \leq 200$ subgroup it will provide 90% power if the recovery rate ratio is 1.34.

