10 STATISTICAL METHODS

10.1 General Considerations

Data summaries and listings will be generated using SAS version 9.4 or a more recent version (SAS Institute Inc., Cary, NC, USA).

The statistical analysis plan and/or the clinical study report will provide additional details of the analysis, which may include details of missing and, if applicable, unused data, as well as additional sensitivity analyses of the primary and secondary variables. The clinical study report will describe deviations from the statistical analysis plan, if any.

The statistical analysis approach will be designed to assess the significance of the primary and first secondary endpoint using the Benjamini and Hochberg method to control the overall trial level alpha level. The statistical analysis approach will be descriptive, exploratory and inferential for the other secondary and exploratory endpoints.

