10.8.1 Primary Efficacy Analysis

Time to recovery of the imputed $PaO_2/FiO_2 \le 200$ subgroup is the primary endpoint and is defined as the number of days from the SFISD to the date of recovery. Failure to recovery and death are both censored at Day 61.

Time to recovery will be displayed using a Kaplan-Meier estimate and will be compared between the 2 treatment groups using a stratified log-rank test stratified by the baseline imputed PaO2/FiO2 of ≤100 vs. >100 with an overall 2 sided alpha level of 0.05 using the Benjamini and Hochberg method.

In addition, the recovery rate ratio and the 95% CI will be estimated using a Cox proportional-hazard model with treatment as the independent variable.

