10.8.2 Secondary Efficacy Analyses

Secondary efficacy endpoints will be defined in more detail in the statistical analysis plan. All-Cause Mortality at Days 60 and 30 will be analyzed for significance along with time to recovery

using the Benjamini and Hochberg method to control overall trial level 2 sided alpha level of 0.05. The additional secondary endpoints defined in Session 10.3 will be compared between the two treatment groups and the analysis will be descriptive, exploratory and inferential.

10.8.3 Mortality at Days 60 and 30

Proportion and 95% CI All-cause mortality at Day 60 and 30 will be displayed using a Colpper-Pearson interval and will be compared between the 2 treatment groups using a Cochran-Mantel-Haenszel test stratified by the baseline imputed PaO2/FiO2 of ≤100 vs. >100.

10.8.4 Proportion of Patients Requiring Invasive Mechanical Ventilation or Dying During the 60 Days from the SFISD

Proportion of patients requiring invasive mechanical ventilation or dying is defined as the proportion at study Day 60. Day 60 rate for each treatment group will be estimated by the Kaplan-Meier procedure. Hypothesis testing will be based on the Kaplan-Meier estimates and standard errors estimated by Greenwood formula.

10.8.5 Proportion of Patients Requiring Invasive Mechanical Ventilation During the 60 Days from the SFISD

Proportion of patients requiring invasive mechanical ventilation is defined as the proportion at study Day 60. Day 60 rate for each treatment group will be estimated by the Kaplan-Meier procedure. Hypothesis testing will be based on the Kaplan-Meier estimates and standard errors estimated by Greenwood formula.

10.8.6 Differences in Outcomes Measured by an 8-Point Ordinal Scale At Day 12

Proportion of patients in each category of 8-point ordinal scale will also be calculated for each treatment group, and odds ratio will be estimated at Day 12. The proportion will be compared between the 2 treatment groups using a proportional odds model with fixed factor of treatment groups.

8-point ordinal scale will be imputed based on LOCF method based on the scale at discharge if the patient is discharged from hospital with the ordinal scale of 7 or 8.

10.8.7 Difference in Outcomes Measured by an 8-Point Ordinal Scale at Day 30

The analysis will be the same as the Day 12 analysis but extended at Day 30.

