8.4.2 Main Analytical Approach

Time to recovery through Day 60 visit will be displayed using a Kaplan-Meier estimate and will be compared between the 2 treatment groups using stratified log-rank test stratified by baseline imputed $\text{PaO}_2/\text{FiO}_2$ screening of ≤ 100 vs. > 100 . Prohibited immunosuppressive medications or immunotherapies, convalescent plasma treatment and treatment discontinuation will be ignored (treatment policy strategy). Death will be treated as not recovered and time to recovery will be censored at Day 65 (composite strategy). Patients, including withdrawal of consent patients, will be censored at the last ordinal scale assessment if no recovery event is observed during the study (administrative censoring). The trial level Type I error of 0.05 between the two tests of the primary endpoint analysis and the key secondary endpoint analysis is controlled using the Benjamini and Hochberg method.

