8.5.2 Main Analytical Approach

Proportion and 95% CI All-cause mortality at Day 60 visit will be displayed using a Clopper-Pearson interval and will be compared between the 2 treatment groups using a Cochran-Mantel-Haenszel test stratified by the baseline imputed $\text{PaO}_2/\text{FiO}_2$ of ≤ 100 vs. > 100 . Prohibited immunosuppressive medications or immunotherapies, convalescent plasma treatment and treatment discontinuation will be ignored (treatment policy strategy).

Patients with unknown death status at Day 60 visit will be treated as alive for the analysis if recovered during the study. Specifically, all patients who recovered, were discharged, and/or had 30 day follow up where they remained recovered, will be imputed at Day 60 as being alive/recovered if data is missing. Patients who discontinued from study before or on Day 1 and Day 60 survival follow up status as unknown are excluded from the primary analysis. This is not expected to introduce a bias in favor of either treatment arm since the clinical status is not likely to be affected within two days by the study treatment administered on Day 1.

To protect the trial level type 1 error rate at $\alpha = 5\%$ (two sided) between the two tests of the primary endpoint analysis and the key secondary endpoint analysis, the Benjamini and Hochberg testing strategy is used. Test statistics for Time to recovery and All-cause mortality at Day 60 are positive correlated and Hochberg testing strategy will protect the trial level type 1 alpha level.

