- Recovery rate ratio 1.05 to <1.34 , increase sample size to 600 for imputed $\text{PaO}_2/\text{FiO}_2 \leq 200$ subgroup
- Recovery rate ratio 1.34 to 1.38 , increase sample size to 500 for imputed $\text{PaO}_2/\text{FiO}_2 \leq 200$ subgroup
- Recovery rate ratio 1.39 to 1.43 , increase sample size to 400 for imputed $\text{PaO}_2/\text{FiO}_2 \leq 200$ subgroup
- Recovery rate ratio ≥ 1.44 , do not increase sample size for imputed $\text{PaO}_2/\text{FiO}_2 \leq 200$ subgroup

The sample size re-estimation rule was updated and a non-binding futility analysis was added prior to the conduct of the interim sample size re-estimation. The updated sample size re-estimation rule was based on the promising zone with re-estimated sample size of 500 patients. The study used a sequential design with O'Brien-Fleming critical boundary ([O'Brien and Fleming 1979](#)) at the interim analysis to control type I error. In case of sample size modification, the final critical boundary will be adjusted to control type I error ([Gao et al., 2008](#)). The detailed promising zone rule is described in the separate interim statistical analysis plan and was finalized before the interim sample size re-estimation.

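### The 90% power for recovery at 320 patients belongs to a single test at 0.05; under the planned Hochberg procedure with Day-60 mortality it is about 84% to 90% at a fixed 320, and the plan does not say so

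*SAP*

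**What the plan says.** SAP 4, in the same words as Protocol 10.2, justifies 320 patients with an imputed PaO2/FiO2 of 200 or less as follows: "A two group log-rank test with a 0.05 two-sided significance level would have 90% power to detect a difference" in a recovery rate ratio of about 1.49. SAP 4 adds that if 600 patients are randomized "it will provide 90% power if the recovery rate ratio is 1.34".

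The analysis sections describe a different test. Protocol 10.1 plans to "assess the significance of the primary and first secondary endpoint using the Benjamini and Hochberg method", and Protocol 10.8.1 compares time to recovery "with an overall 2 sided alpha level of 0.05 using the Benjamini and Hochberg method". SAP 8.4.2 controls "The trial level Type I error of 0.05 between the two tests of the primary endpoint analysis and the key secondary endpoint analysis" by the same method. SAP 8.5.2 repeats this, calls it a Hochberg strategy, and justifies it thus: "Test statistics for Time to recovery and All-cause mortality at Day 60 are positive correlated". It gives no size for the correlation.

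On the sample size rule, SAP 9.1 says: "The updated sample size re-estimation rule was based on the promising zone with re-estimated sample size of 500 patients". It refers to a separate interim SAP for the zone itself.

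**The concern.** A reader will take the 90% as the power of the analysis the trial will run. Labelling mortality as key secondary encourages this: under a fixed sequence the primary endpoint would keep the full 0.05 and 90% would be correct. Under Hochberg it does not keep the full 0.05 in every case. A recovery p-value between 0.025 and 0.05 counts as a success in the stated 90%, but in the plan it counts only if Day-60 mortality is also significant at 0.05.

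The 90% is the only power figure given for the primary endpoint at the planned 320 patients. If mortality has little power, the chance of missing a true ratio of 1.49 at that size is nearer 16% than 10%.

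**Working it through.** **Inputs.** The ratio of 1.49, 320 patients and 1:1 allocation are in SAP 4. No event count stands beside the 1.49 figure, so two are used: 264, from the initial design in SAP 4 (330/400 = 0.825, and 0.825 × 320 = 264), and 266, from the 320-patient row of SAP Table 4. Mortality power and correlation are not given and are varied.

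**Formula.** Power = Φ(½·√d·ln RR − z), with d events; z = 1.9600 for two-sided 0.05 and 2.2414 for two-sided 0.025.

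**Step 1: the plan's own figure.** ln 1.49 = 0.3988.
- d = 264: ½ × 16.248 × 0.3988 = 3.240; 3.240 − 1.960 = 1.280; power 89.97%.
- d = 266: 3.252 − 1.960 = 1.292; power 90.18%.

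The 90% reproduces. The initial design does too: a ratio of 1.43 at 90% power needs 329 events against the 330 stated, with no multiplicity adjustment.

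**Step 2: recovery tested at 0.025.**
- d = 264: 3.240 − 2.241 = 0.998; power 84.09%.
- d = 266: 3.252 − 2.241 = 1.011; power 84.39%.

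The difference from step 1 is 5.8 to 5.9 points.

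**Step 3: the Hochberg rule.** Let Zr and Zm be the two test statistics, bivariate normal. Power for recovery = P(Zr > 2.2414) + P(1.96 < Zr ≤ 2.2414 and Zm > 1.96). The first term is step 2; the second is at most the difference between steps 1 and 2. With 264 to 266 events, correlation 0 to 0.6, and only a mortality benefit counted:

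| Assumed mortality power | Power for recovery |
|---|---|
| no mortality effect | 84.1–84.5% |
| 20% | 84.3–85.6% |
| 50% | 85.3–87.3% |
| 80% | 87.5–89.0% |
| 90% | 88.6–89.6% |
| 99% | 89.9–90.1% |

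Counting significant mortality in either direction adds at most about 0.3 points, and only near no effect.

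**Step 4: ratio with 90% power at 0.025.** ln RR = 2 × (2.2414 + 1.2816)/√d, which gives 1.54 for both 264 and 266 events.

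**Step 5: the 600-patient sentence.** Events are 495 (0.825 × 600) to 503 (the 600-patient row of SAP Table 4). At ratio 1.34, power is 90.2–90.7% at 0.05 and 84.5–85.1% at 0.025.

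**Step 6: allowing an increase to 500.** The zone is not in the documents provided. Assumptions: an increase when conditional power is between a lower limit of 30–50% and an upper limit of 80–90%; interim at information fraction 70/320 to 0.25; the SAP 9.1.1 boundary formula applied from each critical value; futility ignored. By simulation (3 million draws), power at ratio 1.49 is about 91–93% at the 0.05 boundary and about 86–88.5% at the 0.025 boundary. The largest shortfall from 90% is then about 4 points.

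**The case against.** **The 90% is correct as worded.** The sentence names its test, and on that condition the figure reproduces. This stands: a reader might infer a calculation error, and there is none. What is missing is the power of the test that will be used.

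**The true shortfall cannot be fixed from these documents.** It depends on mortality power, correlation and the promising zone, and the interim SAP may hold operating characteristics. This also stands. It is why the result is a range that includes zero, and why the claim is limited to the text provided. A reader might infer that power simply is 84%, or that 90% caps the adaptive design; neither follows. 84% is the lower limit at a fixed 320, and step 6 allows figures above 90%.

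**The event count is itself uncertain.** The 0.825 comes from a 400-patient design that pooled both oxygenation subgroups, which SAP 4 ties to a 30-day study length, while the endpoint now runs through Day 60. With event fractions of 75% to 90% (240 to 288 events), power is 87.1% to 92.3% at 0.05 and 80.2% to 87.3% at 0.025. That movement is about as large as the shortfall, so the reworded sentence must state its event count. It does not close the gap, which exists at any event count.

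**It changes no decision.** SAP 2.0 is dated 17 August 2021 and reports the interim as already done. That limits the weight: this is disclosure, not redesign. But SAP 4 remains the stated justification for the sample size, and correcting it is cheap.

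**Conclusion.** The point holds as a mismatch between the stated power and the planned test. At a fixed 320 patients, ratio 1.49 and 264 to 266 events, unconditional power for recovery under the two-test Hochberg rule is about 84% to 90%. The stated 90% is the upper end, reached only if mortality is almost certain to be significant. The overstatement is 0 to about 6 points at that size, and at most about 4 points under the assumed zones for an increase to 500.

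Three further inferences are tempting but not supported:
- That 84% is the power when mortality turns out non-significant. That holds only at zero correlation, and SAP 8.5.2 asserts a positive one. For mortality power of 80% down to 50%, the conditional figure is 72.6–78.7% at correlation 0.3 and 57.7–73.1% at 0.6.
- That the lower limit is about 80%. This follows only if Protocol 10.8.2, "All-Cause Mortality at Days 60 and 30 will be analyzed for significance along with time to recovery", is read as a three-test family (lowest level 0.05/3, power 80.1–80.5%). Protocol 10.1 names only the first secondary endpoint, and the SAP fixes the family at two tests.
- That SAP 9.1.1 is wrong because it quotes only 1.96. Its formula is general in C_2, and nothing here depends on changing it.

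**What to change.** In SAP 4, replace the 320-patient power sentence with:

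> For a ratio of 1.49 in 320 patients (about 264 to 266 recovery events), power is 90% for a single log-rank test at two-sided 0.05. Under the Hochberg procedure with Day-60 mortality, unconditional power for recovery is between about 84% and 90%, depending on the power for mortality and the correlation of the tests; the ratio with 90% power at level 0.025 is about 1.54. These figures assume no sample size increase.

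Qualify the 600-patient sentence in the same way: about 84.5% to 90% under the Hochberg procedure at ratio 1.34 (about 495 to 503 events). Note there that SAP 9.1 has since updated the rule to 500 patients.

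If Protocol 10.2 is left unchanged, say in SAP 4 that its 90% is the single-test figure, so that the two documents do not appear to disagree. Changing Protocol 10.2 as well would need an amendment under Protocol 11.8, and should then state that the family is recovery and Day-60 mortality.

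The cost is a few reworded sentences in the SAP, with no extra patients and no change to the test or to alpha. The downside is that the stated power becomes less favourable.
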